of how the external light environment impacts sleep), the relationship of sleep with health, function, and well-being and tips for achieving good sleep. Participants will have the option of watching the educational videos during hospitalization or at home for those with internet access and participants will also be given a written summary of the contents of the educational videos.

Phase A participants will then be instructed on how to administer the CC intervention. The CC intervention will consist of a wearable light visor to administer the BLT each morning for 30 minutes after awakening, and the BLB glasses to be worn each night from 8:00pm to bedtime. Instructions on how to use the intervention devices will be offered in person during enrollment, over the phone, or online via Zoom after the participant has returned home.

Visit 1/Baseline: After verbally agreeing to participate and enroll in the study, Phase A participants will be scheduled for Visit 1 (either in person, telephone, or video on Zoom). During Visit 1, participants will complete a questionnaire battery on their sleep, PTSD symptoms, and cardiac anxiety. Participants who were unable to view the educational videos during enrollment will be able to do so during Visit 1.

Phase A participants will receive a wrist-mounted accelerometer (GENEActiv) designed to measure their sleep and physical activity. Coordinators will provide participants with the device and instruct participants to begin wearing it the day following Visit 1. They will be asked to wear this GENEActiv on their wrist for the next 4 weeks. Upon successful completion of Visit 1, Phase A participants will be asked to begin the intervention the following day, starting with BLT in the morning and BLB that night. Use of the intervention will continue daily for the next 4 weeks. Participants will also be asked to complete a paper-based sleep diary/daily-use log, where they will document the times they administered each of the interventions (i.e., time of starting and stopping BLT, time of donning and doffing BLB glasses, and times of going to bed and waking up). Research staff will contact participants weekly to collect the data that were entered in the sleep diary/daily use log, and also to ask about any adverse events or side effects (see below).

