Phase B participants will receive a wrist-mounted accelerometer (GENEActiv) designed to measure their sleep and physical activity. Coordinators will provide participants with the device and instruct participants to begin wearing it the day following Visit 1. They will be asked to wear this GENEActiv on their wrist for the next 4 weeks. Upon successful completion of Visit 1, Phase B participants randomized to the active CC intervention will be asked to begin the intervention the following day, starting with BLT in the morning and BLB that night. Use of the intervention will continue daily for the next 4 weeks. Participants will also

be asked to complete a paper-based sleep diary/daily-use log, where they will document the times they administered each of the interventions (i.e., time of starting and stopping BLT, time of donning and doffing BLB glasses, and times of going to bed and waking up). Phase B participants randomized to the sleep hygiene education control arm will also be asked to wear a GENEActiv for 4 weeks and complete the sleep diary (indicating times of going to bed and waking up) each day. Research staff will contact all Phase B participants weekly to collect the data that were entered in the sleep diary/daily use log, and also ask the participants randomized to the active CC intervention about any adverse events or side effects (see below).

After enrollment, participants will be provided with a pre-paid package which can be used to return the BLT visor, GENEActiv, the sleep diary/daily use log, and the exit interview at the conclusion of Visit 2.

Visit 2: At the end of the intervention period (4 weeks after Visit 1), all Phase B participants (intervention and control arm) will complete Visit 2 in person, over the phone or via Zoom. During Visit 2, participants will complete measures of sleep quality, cardiac anxiety, and PTSD symptoms. Additionally, participants in the active CC intervention group will complete questionnaires about feasibility, acceptability, appropriateness, and usability of the intervention.

Phase B participants will be provided with a pre-paid envelope which can be used to return the study devices, the exit interview, and the sleep diary/daily use log after Visit 2. If the exit interview is not returned, research staff may call the participant to administer the questionnaire over the phone (though this has no bearing on participant compensation).

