Between Visit 1 and Visit 2: For the 4 weeks between Visit 1 and Visit 2, participants in Phase A and participants in the active CC arm group of Phase B, will be instructed to wear the BLT visor for 30 minutes each morning starting after awakening, and to record the time they put them on and remove them each day in their sleep diary/use log. These participants will also be instructed to wear their BLB glasses beginning at 8:00PM each night until they go to sleep, and to record the time they put them on and remove them each day in their sleep diary/use log. Participants will also wear the glasses during any nocturnal awakenings in which a light is turned on, a light-emitting electronic device is used in bed, etc. All participants (in both arms) will also be instructed to record in their sleep diary/use log when they go to sleep and wake up each day. There will be weekly check-ins via telephone call by the research team to remind participants to use the devices and continue to complete the sleep diary/use log. During the check-ins, research staff will collect the data that has been entered in the sleep diary/use log. Additionally, research staff will ask on a weekly basis during the check-in call if the participant has experienced any adverse events or side effects. The research staff will ask "Over the past week, have you experienced any side effects from either of the treatments? If so, please tell us what you experienced. If possible, please tell us which portion of the intervention (light visor or orange-tinted glasses) you believe may have caused this side effect." Any reported adverse events or side effects will be reported to the study PI ([name]), the study physician ([name]) and the study safety officer ([name]).

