Visit 2: Post-Intervention Questionnaires (20 min): A member of the research team (coordinator or PI) will meet with the participant over the phone, via Zoom or in person to administer a series of questionnaires. All participants will complete the same set of baseline questionnaires and only the active CC intervention participants will complete valid, reliable, and pragmatic 4-item surveys on the acceptability, appropriateness, and feasibility of the intervention: (1) Acceptability of Intervention Measure (AIM), (2) Intervention Appropriateness Measure (IAM), and (3) Feasibility of Intervention Measure (FIM).¹⁸ They will also complete the System Usability Scale to assess the intervention usability. The participant will return study devices and materials (in person, if this visit is conducted as such) or will be instructed to return these items by mail using a pre-paid envelope. The items which will be returned include the BLT visor, the GENEActiv, the sleep diary/use logs, and the exit interview.

3. Compensation

Participants will be reimbursed for their time participating in the study in the form of PayCards.

Phase A: Participants in Phase A will receive \$40 for successful completion of Visit 1. They will receive a second payment of \$40 for completion of Visit 2. They will receive a third payment of \$50 for returning the GENEActiv, sleep diary/use log and the BLT visor. All 3 items must be returned in order to be compensated. Compensation for completing all study procedures in Phase A is up to \$130 (including participation and returning study materials/devices).

Phase B: Participants in Phase B will receive \$40 for successful completion of Visit 1. They will receive a second payment of \$40 for completion of Visit 2. They will receive a third payment of \$50 for returning the GENEActiv, sleep diary/use log and the BLT visor. Please note, the BLT visor return is only applicable to the intervention group but additional compensation is not provided for the return of the visor. Participants will receive \$20 for completing the 3-month follow-up assessment (PCL-5 and PSQI questionnaires). Compensation for completing all study procedures in Phase B is up to \$150 (including participation and returning study materials/devices).

All Phase A and Phase B participants will be permitted to keep the study-provided BLB glasses.

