Please note, participants who are determined to be ineligible at any time during the screening questionnaire will not be compensated.

Please note, due to the change in vendor for Columbia University PayCards, current and past participants of both Phase A and Phase B who receive(d) a Bank of America PayCard, will receive a PayCard addendum letter by email and/or mail to ensure they are aware of the card expiration date.

4. Risks

Bright light therapy (BLT): Although extremely unlikely, participants may encounter risks that any person may encounter when engaging in treatment with BLT. BLT side effects can rarely include eye strain, headache, nausea, irritability or agitation. These side-effects are expected to be mild, and to be reversible with cessation of therapy.

Participants are encouraged to stop or reduce their use of light therapy if they experience any side-effect that they perceive as severe. A study physician and a sleep expert (the study PI) will be available by email for questions about side-effects during business hours and participants will also be able to contact

their personal physicians as they would in clinical practice if any questions pertaining to study light therapy arise. Research coordinators will review phone calls and emails at least twice per day and will relay any questions that could relate to patient safety to the study physicians. The presence of adverse events or side effects related to treatment will be assessed on a weekly basis, via phone calls made to participants by research staff.

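### Side effects are actively asked about only in the weekly calls between Visit 1 and Visit 2; no described question at Visit 2 or at the Phase B 3-month contact follows them up, and resolution is not recorded

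*Protocol*

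**What the plan says.** The Phase B overview (Protocol section 2) sets the exposure: "Use of the intervention will continue daily for the next 4 weeks", starting the day after Visit 1. Visit 2 falls four weeks after Visit 1.

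Side effects are solicited in one way. For Phase A, "Research staff will contact participants weekly to collect the data that were entered in the sleep diary/daily use log", and the same contact asks about adverse events. For Phase B, staff make weekly contact and "also ask the participants randomized to the active CC intervention about any adverse events or side effects". Section 3, under the heading for the time between the two visits, repeats that "research staff will ask on a weekly basis during the check-in call if the participant has experienced any adverse events or side effects" and scripts a question about the past week and about which device the participant thinks was responsible. Section 4 (Risks) names the same channel: "The presence of adverse events or side effects related to treatment will be assessed on a weekly basis, via phone calls made to participants".

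Visit 2 is described in both design overviews and again in section 3. The section 3 text reads: "All participants will complete the same set of baseline questionnaires and only the active CC intervention participants will complete" the acceptability, appropriateness and feasibility scales, followed by the usability scale and the return of devices. The Phase B contact three months after treatment appears in the Compensation section as a "3-month follow-up assessment (PCL-5 and PSQI questionnaires", and in the note on baseline questionnaires as the full baseline set. Neither version has a side-effect item.

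On what happens after use stops, section 4 offers an expectation: "These side-effects are expected to be mild, and to be reversible with cessation of therapy". The SAP contains no safety analysis.

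**The concern.** The protocol expects side effects to reverse when therapy stops, yet the solicited safety questions are confined to the treatment weeks. A participant who completes four weeks and has an open complaint at Visit 2 is not, on the described procedures, asked whether it went away. The scripted question covers occurrence and attribution, not resolution.

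The number and days of the calls are also unstated. If the week-4 contact is Visit 2 itself, the last week of exposure may never be asked about.

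At stake is the completeness of the side-effect record from a pilot of a home-based intervention. The primary feasibility proportions are not affected. The protocol does treat at least one BLT effect as serious: its exclusion criteria note that BLT can trigger a manic episode. Screening lowers that risk but does not replace asking at the end of exposure.

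**Working it through.** The plan gives no safety figure to reproduce. The check has two parts: which contacts ask, and how many treatment days the questions reach.

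**Contacts described for Phase B CC participants**

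| Contact | Side-effect question described? | Resolution recorded? |
|---|---|---|
| Weekly calls (sections 2, 3, 4) | Yes, past week | No |
| Visit 2 (sections 2, 3) | No | No |
| Exit interview (section 2) | Content not described | Content not described |
| 3-month contact (section 3; Compensation) | No | No |

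**Treatment days reached**

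Inputs from the documents: 4 weeks × 7 = 28 daily-use days, beginning the day after Visit 1; Visit 2 on day 28, counting Visit 1 as day 0; recall of 7 days per call. The call days are not given, so the schedules below are assumptions. If consecutive calls are no more than 7 days apart and the first is by day 7, the days not asked about are 28 − (day of the last call).

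| Assumed call days | Days not asked about | Share of 28 |
|---|---|---|
| 7, 14, 21 | 28 − 21 = 7 | 7/28 = 25% |
| 7, 14, 21, 27 | 28 − 27 = 1 | 1/28 = 3.6% |
| 7, 14, 21, 28 | 28 − 28 = 0 | 0% |

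Phase B allocates 15 patients 2:1, so about 15 × 2/3 = 10 receive CC. Across them the gap runs from 0 to 10 × 7 = 70 of 10 × 28 = 280 person-days.

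**Illustration for the three-call schedule only**

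Assume a 4-week per-person side-effect risk p, constant hazard and independence between participants. The chance that at least one of 10 has an event in the last week is 1 − (1 − p)^(10/4):

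- p = 5%: 1 − 0.95^2.5 = 12%
- p = 10%: 1 − 0.90^2.5 = 23%
- p = 20%: 1 − 0.80^2.5 = 43%

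The documents give no such rates; these values only show scale. With a call on day 28 the final-week gap vanishes.

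**After treatment ends**

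For someone treated to week 4, the number of post-treatment days covered by a described solicited query is 0 under all three schedules, because every call precedes or coincides with the end of treatment.

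**The case against.** Four points on the other side have force.

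- **A reporting route exists.** A reader might infer that a late event has no way to reach the study team. Section 4 contradicts that: the investigator and a study physician can be reached by email, and coordinators review calls and emails at least twice a day and relay safety questions, with no end date given. Section 3 sends any reported event to the investigator, the study physician and the safety officer. What remains is that these routes wait for the participant to speak up.
- **The final week may be fully covered.** It is tempting to say that a quarter of exposure goes unasked. Weekly calls over four weeks can as naturally mean four calls as three, so 25% is the upper end of a range that starts at zero.
- **Some follow-up after stopping may occur.** Participants are encouraged to stop or reduce light therapy for effects they perceive as severe, and nothing ends their weekly calls. Later calls could show resolution incidentally. The exit interview might also ask, since its content is not described. The documents therefore do not support saying that, on any reading, nobody is asked after cessation.
- **Reversibility is an expectation, not a hypothesis.** A reader might take it as the protocol's reason for rating BLT risk as low. Section 4 also calls the risks extremely unlikely, and the side effects rare and mild, and it does not single out reversibility. Safety is not a stated aim, and about 10 participants could not settle the matter.

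These points limit the size of the gap. They do not supply a solicited question at or after Visit 2 for those who complete treatment, or any record of resolution.

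**Conclusion.** The point holds as a minor gap in safety ascertainment. Solicitation is confined to the weekly calls. Between 0 and 7 of 28 treatment days (0% to 25%) lie outside any recall window, depending on unstated call days. For CC participants treated to week 4, no described solicited query covers the period after treatment, so the expectation of reversibility is not systematically checked.

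This rests on the contacts as described. It would shrink if the calls include one on day 28, or if the exit interview contains a safety item. It does not show that events will be missed, that participants cannot report them, or that the risk statement is wrong.

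**What to change.** Phase A is closed and its follow-up is complete, so the change applies to Phase B.

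1. In the Phase B overview of section 2 and in the Visit 2 text of section 3, state the call days. Add the scripted side-effect question to Visit 2 for CC participants, reworded to cover the time since the last call, with the existing reporting route to the investigator, study physician and safety officer.
2. For each event, record whether it is still open at Visit 2. For open events, record later whether they resolved, and the date.
3. At the existing 3-month contact, ask CC participants about events left open and about any side effects since Visit 2. A one-week recall would be too short there. Note whether the blue-light-blocking glasses are still in use, because participants keep them and exposure may not stop at Visit 2.
4. Add a line to the SAP: report events and their resolution descriptively.

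The risk statement in section 4 need not be replaced. The cost is one question at two contacts already planned and a resolution field: a few minutes per participant, and possibly a slightly higher reported event count. No treatment rule changes.

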Statistical Analysis Plan Cover Page

Official Title of the study: A Pilot Chronotherapeutic Intervention to Improve Sleep Following Acute Coronary Syndrome: The SleepWell Study

NCT number: NCT05299723

Date of the document: July 28, 2023

Statistical Design and Power

Below we outline the statistical approach we will use to investigate the specific aims and associated hypotheses for this pilot study.

Primary Aim: *Determine the feasibility of administering the combined chronotherapy (CC) intervention in individuals who experiences acute coronary syndrome (ACS). We will assess a) feasibility, b) acceptability, c) appropriateness, d) usability, and e) adherence of the 4-week CC intervention in ACS survivors with poor sleep.*

Aim 1 will be tested by assessing the following measures:

- (1) proportion of participants who complete the outcome assessments at study conclusion;
- (2) proportion of participants who report scores ≥ 4 for their final rating of the intervention's feasibility;
- (3) proportion of participants who report scores ≥ 4 for their final rating of the intervention's acceptability;
- (4) proportion of participants who report scores ≥ 4 for their final rating of the intervention's appropriateness for improving sleep;
- (5) proportion of participants who report total scores ≥ 68 for their final rating of the intervention's usability.
- (6) proportion of who report administering the intervention (i.e., morning BLT and evening BLB) on $\geq 50\%$ (and $\geq 75\%$) of the days throughout the 4-wk treatment period.

Statistical approach for Primary Aim. In addition to computing the proportions listed above, we will conduct secondary analyses regarding measures 2, 3, and 4 (feasibility, acceptability, appropriateness) as follows. First, the final assessment for each scale (feasibility, acceptability, and appropriateness) will be identified for each participant (i.e., at study conclusion for participants) to compute a mean for each of the three scales. Second, the mean across participants will be computed for each scale (feasibility, acceptability, and appropriateness). A one-tailed t-test will be conducted comparing the mean for each scale against the comparison value of each 5-point scale's midpoint of 3.

Secondary Aim 1: Determine whether the CC intervention engages its target mechanism: sleep. *We will assess insomnia, sleep quality, and sleep duration at baseline and at the end of the 4-week intervention period, and will evaluate whether the CC intervention leads to greater changes in sleep-related outcomes relative to the control condition.*

Secondary Aim 1 will be tested by assessing the following measures:

- (1) Baseline-to-study conclusion change in insomnia severity (measured as the within-person difference in the total score of Insomnia Severity Index);
- (2) Baseline-to-study conclusion change in global sleep quality severity (measured as the within-person difference in the total score of Pittsburgh Sleep Quality Index [PSQI]);
- (3) Baseline-to-study conclusion change in sleep duration (measured as the within-person difference in the sleep duration subscale of the PSQI);

Statistical approach for Secondary Aim 1. We will test this aim by evaluating the change scores in measures listed above. We hypothesize that the pattern of means will reveal a reduction in insomnia symptom severity, an improvement in global sleep quality, and an increase in self-reported sleep duration in the CC intervention group. As mentioned above, this Phase-I trial is not powered to test the significance of these sleep-related changes.

General Approach. For descriptive statistics, categorical data will be presented as percentages and continuous data will be presented as means with standard deviations for normally distributed measures and as median with interquartile range for measures that are not normally distributed. Checks of assumptions (e.g., normality) underlying statistical procedures will be performed and corrective procedures will be applied (e.g., log transformation or nonparametric tests).

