- (1) Baseline-to-study conclusion change in insomnia severity (measured as the within-person difference in the total score of Insomnia Severity Index);
- (2) Baseline-to-study conclusion change in global sleep quality severity (measured as the within-person difference in the total score of Pittsburgh Sleep Quality Index [PSQI]);
- (3) Baseline-to-study conclusion change in sleep duration (measured as the within-person difference in the sleep duration subscale of the PSQI and actigraphy);

2. Study Design

To achieve these aims, we propose to enroll a total of 20 patients who have experienced an ACS event into this two-phase study. Phase A will be a single-arm open-label study of the home-based CC intervention in 5 post-ACS patients. Phase A will consist of English-speaking patients only. Phase A will primarily assess feasibility of enrollment and administering the intervention. After all 5 Phase A participants enroll and complete the study procedures, we will implement Phase B of the study. Phase B is an RCT in which 15 post-ACS patients will be enrolled and randomized (using a 2:1 allocation) to active CC treatment or sleep hygiene education control group. Phase B will consist of both English and Spanish-speaking patients. Participants cannot enroll in both Phase A and Phase B of this protocol.

Overview of Phase A Study Design:

Screening and consent:

Our recruitment strategy is multi-faceted and will include recruiting NYP patients who experienced an acute coronary syndrome (ACS) event within the past 3 months.

The study team will first confirm eligibility and obtain approval from the treating clinician as described in the Recruitment and Enrollment section to contact the patient and discuss the study. Patients who are interested and verbally consent to the study will undergo a pre-screening questionnaire to determine eligibility. All study procedures can occur in-person, over the phone, or online via Zoom (a web-based, HIPAA-compliant video-conferencing platform associated with Columbia University Irving Medical Center). Participants will complete a screening questionnaire to collect demographics, contact information, and participant sleep quality and habits. Additional eligibility will be determined during the screening questionnaire. Phase A participants will view two educational videos (~5 minutes each in length) that will provide information about the basics of sleep, the regulation of sleep (including aspects

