Patients will be eligible for Phase A if they meet the following criteria: (1) 18 years of age or older, (2) can write, speak and read English, (3) provider and patient confirmed ACS, (4) ACS event occurred within the past 3 months, and (4) presence of insomnia symptoms based on the Insomnia Symptoms Questionnaire, or frequently (3-4 times per week) or always (5-7 times per week) experiencing short sleep duration of 6 hours or less per night.

Participants will be excluded if they have any of the following: (1) severe disabling chronic medical and/or psychiatric comorbidities determined on a case-by-case basis that prevent safe or adequate participation; (2) deemed unable to comply with the protocol (either self-selected or indicated during screening that s/he/they could not complete all requested tasks). This includes, but is not limited to, patients with a level of cognitive impairment indicative of dementia, patients with current alcohol or substance abuse, and patients with severe mental illness (e.g., schizophrenia); (3) unavailable for follow-up for reasons such as terminal illness and imminent plans to leave the United States (as we have migrant or mobile patients due to their citizenship and work issues); (4) Non-English speaking; (5) Lack of reliable phone or e-mail access; (6) History of bipolar disorder (manic episode can be triggered by BLT) or positive screen for bipolar disorder based on the Mood Disorder Questionnaire; (7) Eye disease including glaucoma or retinopathy (BLT contraindications); (8) Blindness; (9) Night shift work schedules; (10) taking any anti-depressant or anti-anxiety medications; (11) taking other medications that increase sensitivity to light (by self-report).

Please note, as of 7/25/2023, Phase A of the study is closed to enrollment. All participant follow-up is complete however, the study team will mail and/or email the Phase A PayCard Addendum letter to ensure they utilize any remaining study funds before the PayCard expires.

Patients will be eligible for Phase B if they meet the following criteria: (1) 18 years of age or older, (2) can write, speak and read English or Spanish, (3) provider and patient confirmed ACS, (4) ACS event occurred within the past 3 months, and (4) presence of insomnia symptoms based on the Insomnia Symptoms Questionnaire, or frequently (3-4 times per week) or always (5-7 times per week) experiencing short sleep duration of 6 hours or less per night.

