After a participant's eligibility is confirmed, the research coordinator will schedule Visit 1 with the participant. Visit 1 can occur either via Zoom Video, telephone, or in person according to participant preference and in consideration of the current institution guidelines related to COVID-19 and social distancing. The research coordinator may provide study devices and materials (e.g., GENEActiv, BLT visor, BLB glasses, and device instructions) while they are still in the hospital, within the next 1-2 weeks post-discharge or at Visit 1 if in person. If Visit 1 is conducted remotely, study devices and materials will be sent to the participant's home address. Participants will view the educational videos (~5 minutes each in length) during the enrollment visit. Participants will also have the option of watching the educational videos at home if they have internet access.

Visit 1: A member of the research team (coordinator or PI) will meet with the participant via Zoom Video, in person, or over the phone to conduct a series of pre-intervention preparation components, which includes a set of baseline questionnaires on sleep, a questionnaire on PTSD symptoms, and a questionnaire on cardiac anxiety. They will then conduct the intervention setup. If participants were unable to watch the educational videos during the enrollment visit, they will have the opportunity to view the video during Visit 1.

Baseline Questionnaires (20 mins): Participants will complete a set of questionnaires to obtain the following measures: severity of insomnia symptoms (7-item Insomnia Severity Index, ISI), self-reported global sleep quality and sleep duration (9-item Pittsburgh Sleep Quality Index, PSQI), PTSD symptoms (17-item PTSD Checklist – Specific, PCL-5), cardiac anxiety symptoms (18-item Cardiac Anxiety Questionnaire, CAQ). Note: These assessments will be completed at baseline (i.e., before intervention begins), 4 weeks later at the end of the intervention period, and in participants who are in Phase B, 3 months after the end of the intervention period.

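### Sleep-duration change is defined on the PSQI duration subscale with no unit or direction; under the usual scoring this is a coarse, reverse-coded stand-in for hours, and hours should be used if the form records them

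*SAP*

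**What the plan says.** The SAP, Secondary Aim 1, measure (3), takes sleep-duration change as "measured as the within-person difference in the sleep duration subscale of the PSQI". The protocol's version, in the Secondary Aim 1 list under section 1, reads "measured as the within-person difference in the sleep duration subscale of the PSQI and actigraphy". Neither gives a unit, a scoring rule or the direction of the score.

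The SAP's statistical approach for this aim says "We will test this aim by evaluating the change scores in measures listed above" and expects "an increase in self-reported sleep duration in the CC intervention group". It names no test for the sleep outcomes and adds that "this Phase-I trial is not powered to test the significance of these sleep-related changes".

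Entry is framed in hours. Under Eligibility Criteria in protocol section 3, a patient qualifies on insomnia symptoms or by "frequently (3-4 times per week) or always (5-7 times per week) experiencing short sleep duration of 6 hours or less per night". The Baseline Questionnaires paragraph says that the PSQI supplies sleep duration by self-report, but not whether the answer is in hours or how it is coded.

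**The concern.** Patients are selected partly on hours of sleep and the hypothesis concerns duration, but the analysed quantity is a subscale score. If that score is banded by the hour, a gain inside a band counts as zero, a few minutes across a cut count as a full point, and patients in the end bands have limited or no room to register change. If it is also reverse-coded, successful treatment gives a negative value on something labelled change in sleep duration, and the plan does not tell the reader so.

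Duration is one of three target-engagement outcomes in a randomised phase of 15 patients. No test is planned, so the estimates are the whole product. A pilot estimate is most useful when its mean and SD are in units that can be carried into the next design, and a change of about a third of a point on a four-level score is not.

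**Working it through.** The plan states no effect size, SD or power for this outcome, so there is no figure to reproduce. The 2:1 split of 15 gives 15 × 2/3 = 10 on combined chronotherapy (CC) and 15 × 1/3 = 5 on control.

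**Assumptions (not in the documents).** Score 0 for >7 h, 1 for 6–7 h, 2 for 5 to <6 h, 3 for <5 h. Baseline hours are normal with mean μ = 5.0 to 6.5 and SD 1. One indirect support for the direction: both documents label measure (2), the PSQI total, as a severity, so a component feeding it would be expected to rise as sleep shortens.

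**Step 1: how the score behaves.** 5.0 to 5.9 h scores 0; 5.9 to 6.0 h scores −1; 6 to 7 h scores 0; 4 to 4.9 h scores 0; 7.5 to 8.5 h scores 0.

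**Step 2: patients with no change in band.** If everyone gains g hours, with g under 1, the unchanged share is

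U = 1 − Σ over c = 5, 6, 7 of [Φ(c − μ) − Φ(c − g − μ)].

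For μ = 5.5 and g = 0.5: 1 − (0.150 + 0.191 + 0.092) = 0.567.

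| μ (h) | U, 30 min | U, 45 min | Already >7 h, 1 − Φ(7 − μ) |
|---|---|---|---|
| 5.0 | 61.5% | 40% | 2% |
| 5.5 | 56.7% | 35% | 7% |
| 6.0 | 56.7% | 37% | 16% |
| 6.5 | 61.5% | 45% | 31% |

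Allowing answers rounded to the half hour, or a baseline SD of 1.3 h, widens the 30-minute range to 57–67%. The last column is the share starting in the best band, who cannot improve on the score.

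**Step 3: the group mean still moves.** A gain under an hour crosses at most one cut, so the mean change is −(1 − U). For 30 minutes in the table that is −0.39 to −0.43 points, and −0.33 to −0.43 with the wider settings.

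**Step 4: precision of the arm contrast.** Add reporting noise of SD 0.5 h at each visit, true-change SD 0.5 h, and half-hour rounding. The variance of change in hours is 3 × 0.5² + 2 × 0.5²/12 = 0.792, so the SD is 0.89 h. A 30-minute arm difference is then 0.5/0.89 = 0.56 SD in hours. Simulating the score from the same model gives 0.43–0.46 SD. Relative efficiency is (score effect ÷ hours effect)²:

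- lowest, μ = 6.5: (0.434/0.560)² = 0.60
- highest, μ = 5.5: (0.463/0.562)² = 0.68

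Across gains of 30 to 60 minutes the range is 0.52–0.68. A second model, with change SD 0.75–1.25 h and μ = 5.5–6.0, gives 0.54–0.68. Overall this is about 0.5–0.7. At 0.60–0.68, 15 patients carry the information of 15 × 0.60 = 9 to 15 × 0.68 = 10.

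**Step 5: can another source stand in?** The protocol's Phase B overview starts wrist-device wear the day after Visit 1, the same day CC treatment starts, so no pre-treatment actigraphy is described. The SAP drops actigraphy from measure (3). Diary bed and wake times are described only between Visits 1 and 2. The PSQI, given at Visits 1 and 2, is the only measure of sleep duration in the outcome set with a described pre-treatment value.

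**The case against.** The strongest objection is that the coding comes from outside the documents: four levels, the cuts, the reversal and the recording of hours are all absent from them. This stands. The figures are conditional on that coding, and the form must be checked first.

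A reader might infer that the hypothesis has the wrong sign. The documents do not support that. It predicts longer self-reported sleep, not a higher score, just as the same sentence predicts better sleep quality on a measure labelled as a severity. Longer sleep with a lower score agrees with it. What is missing is a stated direction.

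A reader might also infer that real gains are missed altogether. They are not: the SAP looks at the pattern of means, and step 3 shows the mean moving. The share unchanged is an individual-level count from a model in which everyone gains the same amount.

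Nor should the room-to-improve argument be pressed. Short-sleep entry covers 5–7 nights a week as well as 3–4, and the share starting above 7 h is 2–16% unless the mean is as high as 6.5 h.

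Finally, this is an unpowered secondary outcome in a feasibility pilot. With 10 against 5 patients and an illustrative two-sided 5% t-test, power for a 30-minute gain is 10–20% in hours and 8–14% on the score, so neither supports inference. That limits the importance of the point. It does not remove the loss of precision and of readable units in the estimates the pilot will report.

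**Conclusion.** The point holds in a limited form. Both documents put sleep-duration change on a subscale with no unit or direction. If the usual 0–3 reverse-coded hourly banding applies, the score is a coarse substitute for the hypothesised quantity. With baseline mean 5.0–6.5 h and SD 1 h, about 57–62% of patients with a true 30-minute gain stay in the same band, and relative efficiency for the arm contrast is about 0.5–0.7. The result also cannot be expressed in minutes.

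What rests on the documents alone is narrower: the missing unit and direction, the difference between protocol and SAP over actigraphy, and the absence of any described pre-treatment actigraphy. The effect is on estimation and description, not on a planned test.

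**What to change.** 1. Check that the PSQI form in use records hours of sleep, and how the duration component is scored.
2. If it does, define measure (3) in both documents as change in self-reported hours of sleep per night from the PSQI duration item, Visit 2 minus Visit 1, positive for longer sleep.
3. Keep the duration component for computing the PSQI global score and as a supportive result.
4. Once the scoring is confirmed, state that higher component, PSQI global and ISI scores are worse.
5. Reconcile actigraphy: either restore it to the SAP or remove it from the protocol's measure (3). If it is kept, say that no pre-treatment recording is described, so a within-person change from baseline cannot be formed from wear that starts with treatment.

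The redefinition costs one line of text, plus a short note on direction and actigraphy. If the form records hours, no new data, visit or patient is needed. The outcome remains descriptive and unpowered after the change.
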